9.2.1 Primary Efficacy Endpoint

Primary Efficacy Estimand Description	Estimand Attributes
In adult hemodialysis patients with chronic kidney disease and associated moderate to severe pruritus, 2 nemolizumab dosing schedules ^[1] compared to placebo by the difference in proportions of responders where response is defined as an improvement from baseline of WI NRS ≥ 4 at Week 12 without use of rescue therapies and without treatment discontinuation due to lack of efficacy or AE/death related to study drug	Treatment Conditions: initial dose of nemolizumab (60 mg) or placebo at baseline, then nemolizumab (30 mg or 60 mg) or placebo Q4W at Weeks 4 and 8 via subcutaneous injection. Population: adult hemodialysis patients with chronic kidney disease and associated moderate to severe pruritus (will be estimated in the Intent-to-Treat analysis set). Variable: a binary composite response where: Responder is defined as an improvement ≥ 4 in WI NRS from baseline at Week 12 without use of rescue therapies and without treatment discontinuation due to lack of efficacy or AE/death related to study drug. Non-responder is defined as an improvement < 4 in WI NRS from baseline at Week 12 or use of rescue therapies or treatment discontinuation due to lack of efficacy or AE/death related to study drug. Strategies for Intercurrent Events: A composite strategy was chosen for the use of rescue therapies and treatment discontinuation due to lack of efficacy or AE/death related to study drug; in case of use of rescue therapies or treatment discontinuation due to lack of efficacy or AE/death related to study drug, subjects will be considered as treatment failures in the binary composite response. In the case of treatment discontinuation for any other reason, a treatment policy strategy will be used and observed after discontinuation data (if available) will be used. Summary measure: treatment difference of nemolizumab from placebo in proportions of responders

[1] Dosing schedules compared to placebo Q4W are an initial SC dose of nemolizumab (60 mg) at baseline then either 30 mg or 60 mg Q4W at Week 4 and Week 8.

[figure not shown]
Abbreviation(s): WI NRS = Worst Itch Numeric Rating Scale; Q4W = Every 4 Weeks

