19.7 Handling of Missing Data

Missing data for dichotomous efficacy endpoints will be imputed using multiple imputations (MI) under missing at random (MAR) assumption for the primary/main analysis. Dichotomous endpoints will be calculated from the underlying imputed variable.

For the sensitivity analyses of the primary endpoint, missing data will be imputed using a copy reference (CR) approach under missing not at random (MNAR) assumption (dichotomous endpoints will be calculated from the underlying imputed variable) and as "Non-responder"; moreover a Tipping Point analysis under MNAR assumption will be carried out.

For the sensitivity analyses of the key secondary efficacy endpoints, missing data will be imputed using a CR approach under MNAR assumption (dichotomous endpoints will be calculated from the underlying imputed variable) and as "Non-responder".

Missing data of continuous efficacy endpoints and QoL/Health Outcome endpoints will be imputed using MI under MAR assumption.

For the multiple imputation, the MI procedure of the SAS system will be used to generate sets of data with missing values imputed from observed data. It is expected that the pattern of missing data will be monotonic, with slight deviations being corrected by the Markov Chain Monte Carlo (MCMC) method of the MI procedure. A predictive mean matching method will be used for the continuous data with the following covariates included in the imputation model: non-missing data from earlier time points. Separate imputations by treatment group will be carried out. Changes and percent changes from baseline and dichotomous endpoints will be calculated from the imputed data.

Subjects who took rescue therapies as defined in Section 12.5.1.2 or discontinued treatment due to lack of efficacy or AE/death related to study drug will be considered as treatment failures, efficacy data collected after the use of rescue therapies or treatment discontinuation due to lack of efficacy or AE/death related to study drug will be set to the worst possible value and subject's binary response will be imputed as "Non-responder" prior to conducting the MI and Tipping Point analysis.

Further details will be provided in the SAP.

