3.2 Study Endpoints

3.2.1 Primary Efficacy Endpoint

[figure not shown]
The primary efficacy endpoint is the proportion of subjects with an improvement of Worst Itch Numeric Rating Scale (WI NRS) ≥ 4 from baseline at Week 12 without use of rescue therapies and without treatment discontinuation due to lack of efficacy or AE/death related to study drug. Subjects who took rescue therapies or discontinued treatment due to lack of efficacy or AE/death related to study drug will be considered treatment failures (see [Table 6](#) for full details of the primary estimand). Note that this combines the outcome with intercurrent events by defining a binary composite response.

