- b: For week 12 weekly average, if fewer than 4 daily WI NRS/SD NRS scores for the 7-day period are available, the interval upper bound will be extended for 5 additional days, one day at a time, until 4 daily WI NRS/SD NRS scores are available. If after extending the upper bound fewer than 4 daily WI NRS/SD NRS scores available, the interval lower bound will be extended for 5 additional days, one day at a time, until 4 daily scores are available. If after the interval extension fewer than 4 daily WI NRS/SD NRS scores are available, the week 12 weekly average WI NRS/SD NRS will be considered missing.

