4.11.4 Safety Set

The Safety Set includes all randomized subjects who receive at least one dose of study drug. All safety data will be summarized based on the Safety Set. Subjects will be summarized according to their actual treatment group.

CC1

5 Estimands

The estimands for primary and key secondary endpoints provide precise descriptions of the treatment effect reflecting the clinical questions posed by the trial objectives. They summarize at a population level what the outcomes would be in the same patients under different treatment conditions being compared.

The intercurrent events are events occurring after treatment initiation that affect either the interpretation or the existence of the measurements associated with the clinical question of interest. It is necessary to address intercurrent events when describing the clinical question of interest in order to precisely define the treatment effect that is to be estimated.

The intercurrent events identified for this study and the estimands for primary and key secondary endpoints are defined in the following tables.

Table 5 List of Intercurrent Events

Intercurrent Event	Strategy to Deal With Intercurrent Event Within Analysis	Assessment of Subjects
Rescue therapy	Composite strategy	Subjects will be considered as treatment failures. The values of the variable of

Intercurrent Event	Strategy to Deal With Intercurrent Event Within Analysis	Assessment of Subjects
		interest collected after the use of rescue therapies will be set to the worst possible value and subject's binary response will be imputed as "Non-responder"
Treatment discontinuation due to lack of efficacy or AE/death related to study drug	Composite strategy	Subjects will be considered as treatment failures. The values of the variable of interest collected after treatment discontinuation due to lack of efficacy or AE/death related to study drug will be set to the worst possible value and subject's binary response will be imputed as "Non-responder"
Treatment discontinuation due to any other reason	Treatment-policy strategy	The values of the variable of interest are used regardless of the occurrence of treatment discontinuation

Table 6 Estimand of Primary Efficacy Endpoint

Primary Efficacy Estimand Description	Estimand Attributes

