Estimand 1: In adult hemodialysis patients with chronic kidney disease and associated moderate to severe pruritus, 2 nemolizumab dosing schedules ^[1] compared to placebo by the difference in proportions of responders where response is defined as an improvement from baseline of WI NRS ≥ 4 at Week 12 without use of rescue therapies and without treatment discontinuation due to lack of efficacy or AE/death related to study drug	
Treatment Conditions: initial dose of nemolizumab (60 mg) or placebo at baseline, then nemolizumab (30 mg or 60 mg) or placebo Q4W at Weeks 4 and 8 via subcutaneous injection.
 
Population: adult hemodialysis patients with chronic kidney disease and associated moderate to severe pruritus (will be estimated in the Intent-to-Treat analysis set).
 
Variable: a binary composite response where: Responder is defined as an improvement ≥ 4 in WI NRS from baseline at Week 12 without use of rescue therapies and without treatment discontinuation due to lack of efficacy or AE/death related to study drug. Non-responder is defined as an improvement < 4 in WI NRS from baseline at Week 12 or use of rescue therapies or treatment discontinuation due to lack of efficacy or AE/death related to study drug.
 
Strategies for Intercurrent Events: A composite strategy was chosen for the use of rescue therapies and treatment discontinuation due to lack of efficacy or AE/death related to study drug; in case of use of rescue therapies or treatment discontinuation due to lack of efficacy or AE/death related to study drug, subjects will be considered as treatment failures in the binary composite response. In the case of treatment discontinuation for any other reason, a treatment policy strategy will be used and observed after discontinuation data (if available) will be used.
 
Summary measure: treatment difference of nemolizumab versus placebo in proportions of responders

[1] Dosing schedules compared to placebo Q4W are an initial SC dose of nemolizumab (60 mg) at baseline then either 30 mg or 60 mg Q4W at Week 4 and Week 8.

Summary of estimation is provided in section [Appendix B](#).

Composite binary response variables are defined in a similar manner as in the primary efficacy estimand for the following key secondary estimands where all estimands attributes are as per Estimand 1 except for the variable definition as reported below.

Table 7 Estimands for Key Secondary Efficacy Endpoints

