9.1.1 Primary Analysis of the Primary Efficacy Endpoint (Estimand 1)

A summary will be provided for the primary efficacy endpoint without any imputation of missing data. Note that subjects who took rescue therapies at any point up to and including Week 12 are considered as treatment failures in this endpoint.

In the main statistical analysis described below, missing WI NRS weekly average values will be imputed for the ITT set using multiple imputations (MI) under missing at random (MAR) assumption. Worst values are assumed after use of rescue therapy or treatment discontinuation due to lack of efficacy or AE/death related to study drug prior to imputation. Dichotomous endpoints will be calculated from the underlying imputed variable. See [Appendix C](#) for details about Multiple Imputation.

The proportion of subjects with an improvement at Week 12 of WI NRS ≥ 4 from baseline without use of rescue therapies and without treatment discontinuation due to lack of efficacy or AE/death related to study drug will be analyzed in the ITT Set for each multiply imputed dataset, using the Cochran-Mantel-Haenszel (CMH) test stratified by analysis center; strata-adjusted difference in proportions between treatment groups (Nemolizumab – Placebo) and the 97.5% confidence interval (CI) of the difference will be based on the large sample approximation method for binary data using Mantel-Haenszel strata weights⁸ and the Sato variance estimator⁹. This analysis will be performed for both dosing schedules compared to placebo using the “Commonriskdiff” and “CL=MH” options in SAS PROC FREQ. Proportions and strata-adjusted difference in proportions will be pooled using Rubin’s method. Results from the CMH analysis will be combined using the Wilson-Hilferty transformation as described in the Bohdana Ratitch, et al. paper¹⁰ to produce a pooled CMH test p-value.

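### A death not related to study drug has no workable intercurrent-event rule in the readable text, so a subject who died before Day 85 can count as a Week 12 responder

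*SAP*

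**What the plan says.** SAP Section 5 defines intercurrent events as "events occurring after treatment initiation that affect either the interpretation or the existence of the measurements associated with the clinical question of interest" and says they have to be addressed. Table 5 then lists three: rescue therapy; treatment discontinuation for lack of efficacy or for a drug-related AE or death; and treatment discontinuation for any other reason. The first two are composite failures. For the third the table says "The values of the variable of interest are used regardless of the occurrence of treatment discontinuation", and Table 6 adds that "a treatment policy strategy will be used and observed after discontinuation data (if available) will be used".

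Death appears only with the drug-related qualifier. SAP 3.2.1: "Subjects who took rescue therapies or discontinued treatment due to lack of efficacy or AE/death related to study drug will be considered treatment failures". Protocol 9.2.1 requires response "without treatment discontinuation due to lack of efficacy or AE/death related to study drug".

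The ITT set keeps everyone randomized. For the primary analysis (SAP 9.1.1), "missing WI NRS weekly average values will be imputed for the ITT set using multiple imputations (MI) under missing at random (MAR) assumption", and response is derived from the imputed score. Protocol 19.7 bases the imputation on "non-missing data from earlier time points. Separate imputations by treatment group will be carried out". For the Week 12 average, if fewer than four daily scores exist, the window is first extended forward; then "the interval lower bound will be extended for 5 additional days, one day at a time, until 4 daily scores are available" (SAP 4.10, Table 4 footnote b). Week 4 has no extension.

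**The concern.** Treatment policy needs a value after the event, and death leaves none. It is the clearest case of an event that affects whether the measurement exists, which the SAP's own definition covers. Unrelated deaths are foreseeable: Protocol 8.1 associates pruritus in dialysis patients with higher mortality risk.

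Without a rule, the general machinery takes over. Either the missing Week 12 average is imputed from the subject's earlier scores and own arm, or the last diary days before death supply an observed average. Both routes can yield a responder who was dead at the target day. Whether a death counts as failure would then turn on a relatedness judgment.

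**Working it through.** **1. Which rule applies.** The last injection is at Week 8 (Day 57). A death before that ends treatment and fits the any-other-reason row. After Day 57 all scheduled dosing is complete. SAP 6.1 separates completing treatment from completing the treatment period, so it is unclear whether a later death is a discontinuation at all. If not, no Table 5 row applies. Neither reading makes the subject a non-responder.

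**2. What the window rule returns for WI NRS at Week 12.** Inputs (SAP 4.10): evening window Days 78–84, at least 4 scores, backward extension to Day 73. Assumption: diary complete to the day before death. Forward extension adds nothing.

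| Day of death | Scores used | In Days 78–84 | Week 12 average |
|---|---|---|---|
| up to 76 | at most Days 73–75 (3) | 0 | missing, imputed under MAR |
| 77 | 73–76 | 0 | observed by extension |
| 78 | 74–77 | 0 | observed by extension |
| 79 | 75–78 | 1 | observed by extension |
| 80 | 76–79 | 2 | observed by extension |
| 81 | 77–80 | 3 | observed by extension |
| 82, 83, 84 | 78 to day before death | 4, 5, 6 | observed, ordinary window |

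SD NRS uses the morning window, Days 79–85, so each range moves one day: missing up to Day 77, extended on Days 78–82, ordinary on Days 83–84. At Week 4 an average exists for deaths from Day 26 (WI NRS, Days 22–25 = 4 scores) or Day 27 (SD NRS, Days 23–26 = 4 scores); earlier deaths are imputed.

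**3. What the planned sensitivity analyses reach (SAP 9.1.2).** Sensitivity Analysis 2 scores missing values as non-response, so it covers deaths up to Day 76; the tipping point varies the same subjects. Copy reference also acts only on missing values and can still impute a response. Sensitivity Analyses 4, 5 and 6 drop the extension, so deaths on Days 77–80, 77–79 and 77–78 respectively also become missing, but are then imputed under MAR.

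**4. Size.** The plan's own figure first: 84 per arm, 50% v 20%, two-sided alpha 0.025, pooled normal approximation.

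Power = Φ{[d − z·√(2p̄(1−p̄)/n)] / √[(p₁q₁+p₀q₀)/n]}, with d = 0.30, p̄ = 0.35, z = 2.241:
(0.30 − 2.241 × 0.0736)/0.0699 = 1.93, giving 97.3%. The stated power of at least 90% holds.

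Now count unrelated deaths as failures. If those subjects would otherwise have counted as responders at their arm's planning rate, the difference falls by 0.50·q_active − 0.20·q_placebo, where q is the share who died. All shares are assumed.

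| Deaths before Day 85 (assumed) | Rates | Fall in difference (points) | Power |
|---|---|---|---|
| none | 50 v 20 | 0 | 97.3% |
| 1% in each arm | 49.5 v 19.8 | 0.3 | 97.1% |
| 3% in each arm | 48.5 v 19.4 | 0.9 | 96.6% |
| 5% in each arm | 47.5 v 19.0 | 1.5 | 96.1% |
| 4 on one active arm, 0 on placebo | 47.6 v 20 | 2.4 | 94.7% |
| the same, all 4 otherwise responders | 45.2 v 20 | 4.8 | 90.2% |
| 0 on active, 4 on placebo | 50 v 19.0 | −0.95 | 98.2% |

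Each death moves the crude difference by at most 1/84 = 1.19 points. The direction reverses when q_placebo exceeds 0.50/0.20 = 2.5 times q_active; 2 active and 5 placebo deaths give (0.50×2 − 0.20×5)/84 = 0.

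**5. Can one subject matter?** Only near the boundary: unstratified, 17/84 v 30/84 gives p = 0.0255 and 17/84 v 31/84 gives p = 0.0168, either side of 0.025.

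**The case against.** **Appendices B and C.** The SAP refers estimation and imputation details to them, and both are redacted. A rule for death may be there. This stands as a limit on the claim, although Tables 5–7, which define the estimands, are readable and contain no such rule.

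**Existing cover.** Sensitivity Analysis 2 already scores every death up to Day 76 as non-response. Only Days 77–84 escape it for WI NRS, 8 of 84 days; with a uniform hazard and 1–5% mortality (both assumed) that is 84 × 0.01 × 8/84 = 0.08 to 84 × 0.05 × 8/84 = 0.4 subjects per arm. If death counts as a discontinuation, the per-protocol analysis also leaves these subjects out. This stands, but the primary analysis is unchanged by it, and no planned ITT analysis treats death as failure once an average can be calculated.

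**Wording.** The drug-related qualifier may attach only to death and not to AE. A discontinuation coded to a fatal AE might then already be a failure. The text does not settle this.

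**Readings that go too far.** A reader might infer that the plan definitely assigns every unrelated death to treatment policy; after the Week 8 injection that is open. A reader might infer a bias towards nemolizumab or a threat to power; the direction depends on how deaths split between arms, and no scenario shown falls below 90%. A reader might also want deaths on the target day included; a death on Day 85 or Day 29 can leave all seven evening scores in the ordinary window, so the problem does not extend that far.

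**Conclusion.** The point holds as a minor defect in the estimand definition. On the readable text, an unrelated death before the target day has no strategy that can be carried out, and the primary and key secondary analyses can credit a response to a subject who had died. The consequence is small and its sign is not fixed. The figures rest on assumed death shares, the 50%/20% planning rates (the documents do not say whether these already allow for deaths), complete diaries to the day before death, and crude rather than centre-stratified differences. The reason to act is that a choice about subjects who died should be made while blinded and should not depend on a causality call or on which diary days happen to exist.

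**What to change.** In SAP 3.2.1, 4.7, Tables 5–7 and 9.1.1, and in the matching protocol text (Synopsis, 9.2.1, 19.3.1, 19.7, 19.9), list death from any cause before the target study day (before Day 85 for Week 12, before Day 29 for Week 4) as its own intercurrent event with a composite strategy: non-responder, set before multiple imputation, even if a weekly average can be calculated. Leave the rescue and other discontinuation rows unchanged. State whether the drug-related qualifier applies to both AE and death.

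Cost: this changes the primary and key secondary estimands, so it needs a protocol amendment as well as a SAP update (SAP 16; approvals under Protocol 20.7.1 if classed as substantial), before unblinding. The estimated difference may become slightly less favourable. The rule overrides some real in-window scores: for WI NRS, deaths on Days 79–84 (Week 12) and 26–28 (Week 4); for SD NRS, deaths on Days 80–84 and 27–28. No new data are needed.

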6.1 Disposition

Subject disposition including the number and percentages of subjects for the following categories will be summarized in a table:

- screen failure/not assigned subjects
- screen failure/not assigned subjects due to COVID-19

- randomized subjects
- treated subjects
- subjects who completed the treatment
- subjects who terminated treatment early
- subjects who terminated treatment early due to COVID-19
- subjects who completed the treatment period
- subjects who terminated treatment period early
- subjects who terminated treatment period early due to COVID-19
- subjects who completed the study
- subjects who terminated study early
- subjects who terminated study early due to COVID-19

The reasons for screen failure, early treatment termination and early study termination will be summarized. Subjects affected by COVID-19 related study disruptions, COVID-19 related study disruptions impacting efficacy and COVID-19 related study disruptions impacting safety will be summarized. The percentages of screen failure and subjects randomized will be calculated based on number of subjects screened and other percentages will be based on the number of subjects in the ITT Set.

The reasons for study and treatment discontinuation will also be summarized in the aforementioned table.

Subject disposition data will be presented in a listing. A corresponding listing will be provided for screen failures, subjects with early treatment termination and for subjects with early study termination. Subjects affected by COVID-19 related study disruptions will be presented in a listing. A summary of inclusion/exclusion criteria not met will be presented for all screened subjects. Details of inclusion/exclusion criteria not met will be provided in a listing for the screened set.

6.2 Protocol Deviations

All deviations will be identified, evaluated, and closed prior to database lock. Deviations from the protocol will be assessed as “Major” (or equivalently “Significant”) and “Minor” (or equivalently “Not Significant”) in cooperation with the sponsor. A case-by-case decision regarding exclusions of subjects from the PP Set will be made in a blind data review meeting which will take place prior to database lock and study unblinding.

All major protocol deviations will be summarized by category and by treatment in a table for the ITT Set. The major deviations which lead to exclusion from the PP Set will be summarized in a separate table. All protocol deviations (major and minor) will be listed with major protocol deviations which would lead to exclusion from the PP Set being flagged. All major COVID-19 related protocol deviations will be summarized by

category and all COVID-19 related protocol deviations will be flagged in the corresponding listing.

7 Demographics and Baseline Characteristics

